## 2.2 *Preliminary Data:*

Members of our research team have made key contributions to the field's understanding of the Chinese HIV epidemic, prevention seeking barriers among MSM, and the role of stigma plays in both phenomena. Co-PI [name] and project consultant [name] have both successfully implemented use of unannounced SP approaches for evaluation of healthcare quality, including one application to

PROTOCOL TITLE: Standardized Patients to Address Intersectional Stigma  
VERSION DATE: 07/23/2019

assess HIV stigma in China. These projects demonstrate the feasibility of our approach and provide our team with a wealth of knowledge on best practices. [name] extensive research on HIV-related stigma in Chinese healthcare settings underlies the central justifications of this proposal and driving the central hypothesis that its remedy will lower HIV testing barriers for marginalized communities.

In preparation for the current study, the research team previously conducted preliminary pilot activities from September 2018 to January 2019 in Guangzhou, China. We enlisted local stakeholders (MSM, PLWHA, and STD providers) to provide input on preliminary study materials such as disease case scripts, recruited and trained 4 SPs, and conducted 17 total visits with 10 local consenting STD clinics. Though the sample size is too small to draw population level conclusions, instances of both positive and negative interactions with providers were documented by our SPs. The pilot study also allowed the team to resolve logistical challenges (e.g. consent procedures, number of clinic visits to be conducted in a day) and to monitor for potential adverse events, of which none were reported.

### 2.3 *Existing Literature:*

**Limitations to measuring of Stigma Experienced in Healthcare Settings:** Existing studies have documented how stigma towards PLWH and marginalized groups including sexual minorities impede access to the HIV prevention continuum at multiple points. An extensive body of literature documenting past stigma reduction interventions suggests that these efforts have had moderate to mixed success. Yet common across the literature is the collective uncertainty about the state of the science given issues with existing approaches to measurement of stigma. Nearly all studies rely on the self-reported attitudes and beliefs among providers regarding PLWH or other associated groups, an approach fraught with recall and social desirability bias. Alternative approaches include direct observation of provider behaviors or monitoring of the patient population for reporting of adverse provider interactions. But both approaches face their own limitations, as providers have known tendencies to alter behaviors under observation (the Hawthorne effect); whereas the lack of standardization across patient-reported events makes it difficult to draw firm conclusions about discriminatory treatment.

**Standardized Patients to Measure Care Quality:** A key feature of medical training in many settings, SPs are an increasingly common tool for researching healthcare quality. Their ability to objectively document provider behaviors through unannounced visits to practices presents a simple solution to the longstanding challenges of stigma measurement such as low provider willingness to self-report discriminatory behaviors or the Hawthorne effect. Studies have used unannounced visits from SPs to evaluate the quality of care received by patients in the US and several low and middle-income countries including China.

**Experimental Audits:** Our use of the unannounced SPs in an experimental audit approach (common in social science studies of race and sex discrimination) by randomly varying the sexual orientation and HIV status of each SP case scenario. Measuring stigma as both a healthcare quality index score and through documentation of adverse clinical encounters (e.g. care refusal, discriminatory language) provides quantitative and qualitative measures of sexual, HIV, and intersectional stigma.

#### 2.4 Research Team

This research will be carried out under the auspices of a multi-PI structure, co-led by co-PI's [name] of the University of Minnesota Twin Cities and [name] of the University of North Carolina Chapel Hill.

**Administration:** Both PIs (Drs. [name] and [name]) will provide oversight of the entire program and development and implementation of all policies, procedures and processes. In these roles, they will be responsible for the implementation of the scientific agenda and ensure that systems are in place to guarantee institutional compliance with US and Chinese laws as well as DHHS and NIH policies, including protection of human subjects

PI#1 [name] will serve as contact PI and will assume fiscal and administrative management for this project. She will be responsible for communication with NIH and submission of annual reports. She will also be responsible for implementation of all human subject research approvals at the University of Minnesota and Guangdong Center for STD Control and Prevention in China.

PI#2 [name] will be responsible for development and adherence to the study protocol and will maintain routine communication with local study staff to monitor for any adverse events related to the study. He will also be responsible for implementation of all human subject research approvals at the University of North Carolina.

**Communication and coordination:** The PIs will be responsible for overall conduct of the study. During the initial study period, the PIs will conduct weekly meetings with all the co-investigators to discuss study design and research implementation. Subsequently, weekly meetings will be held either by phone, email, Skype conference, or in person for the discussion of project operations and other activities. Throughout the study implementation period the PIs will conduct weekly calls with local study staff and co-Is based at the study site in Guangzhou to ensure adherence to the study timeline, maintain protocol standards, and to address any issues that may arise. The two PIs will develop a comprehensive data analysis plan to be presented to all co-investigators prior to start of analyses. The PIs will work together to discuss any changes in the direction of the research projects. A publication policy will be established based on the relative scientific contributions of the PIs and key personnel. [name] will serve as the contact PI and be responsible for submission of progress reports to NIH and all communication.

**Conflict Resolution:** If a potential conflict develops, the PIs shall meet and attempt to resolve the dispute. The PIs have worked successfully together for the past several years and there is very low probability that differences of opinion cannot be managed effectively between them. If they fail to resolve the dispute, the disagreement will be referred to an arbitration committee consisting of two impartial senior executives from the University of Minnesota and the University of North Carolina and a third impartial senior executive mutually agreed upon by both PIs. No members of the arbitration committee will be directly involved in the research grant or disagreement.

**Change in PI Location:** If a PI moves to a new institution, attempts will be made to transfer the relevant portion of the grant to the new institution. In the event that a PI cannot carry out his/her duties, a new PI will be recruited as a replacement at one of the participating institutions.

### 3.0 Study Endpoints/Events/Outcomes

#### 3.1 Primary Endpoint/Event/Outcome

Our primary endpoint of the RCT phase of the study will be the quality of healthcare received by SPs in each clinical encounter with an enrolled provider. As a measure of the quality of healthcare provided in each interaction between physicians and standardized patients, we will create an index using 38 items from the structured post-interaction survey questionnaire administered to SPs following each unannounced visit. Individual items will be combined into a global index,  $\bar{s}_i$ , which is calculated as a weighted average of all 38 items, for which weights are calculated as the sum of its row entries in the inverted covariance matrix as follows:

$$\bar{s}_i = (1' \hat{\Sigma}^{-1} 1)^{-1} (1' \hat{\Sigma}^{-1} y_i)$$

where 1 is a column vector of 1s,  $\hat{\Sigma}^{-1}$  is the inverted covariance matrix, and  $y_i$  is a column vector of all items for individual  $i$ .

Using the analysis approach presented in section 17.3, we will estimate the impact of the intervention on the extent to stigma faced by SPs when presenting as MSM or HIV infected patients relative to the "standard" care experienced by the referent case scenarios of a straight, HIV uninfected man.

#### 3.2 Secondary Endpoint(s)/Event(s)/Outcome(s):

Three secondary endpoints will be collected.

The first will take the form of findings from debrief sessions (i.e. structured interviews) with SPs that will be administered by another study team member immediately following each unannounced visit. This qualitative data is intended to identify emergent episodes of adverse care not captured by the healthcare quality checklist used to quantify the primary endpoint. Findings will take the form of a written report to describe patterns and themes emergent in the interviews, with direct quotes to illustrate concepts where helpful.

The second endpoint will be the aggregate clinic-level number of HIV tests conducted in each enrolled clinic during the study period. This data will be abstracted from the provincial case report system.

The third endpoint will be the qualitative data collected through in-depth interviews with our SPs after their participation in each round of clinic visits (baseline and follow-up). The collected data will provide insight into how their sexual identity and experience in community activities may motivate their participation in a research project like ours, and how they may change their views regarding stigma after their study engagement. Findings will take the form of transcribed scripts of recorded interviews.

### 4.0 Study Intervention(s)/Interaction(s)

#### 4.1 Description:

As described in Section 1.1, the main study activities associated with the RCT phase of this project and this protocol involve Stage 1) implementation of the stigma reduction intervention and Stage 2) follow-up data collection using the unannounced SP visit approach.

PROTOCOL TITLE: Standardized Patients to Address Intersectional Stigma  
VERSION DATE: 07/23/2019

The main study activities associated with Stage 1 will involve administration of the intervention. The intervention design is largely informed by the Information-Motivation-Behavioral Skills model of behavior change; final details of the intervention design will also be informed by feedback from study team members and each of the two CABs. Information related programming will involve didactic sessions to inform providers on clinical diagnosis and management of common STIs and HIV/STI epidemiology with a focus on its public health impact on marginalized populations including MSM and PLWH. Motivation related sessions will explore providers' intrinsic motivations for practicing medicine and use group discussions to explore their self-perceived roles in addressing the HIV/STI crisis, particularly in socially marginalized groups including MSM. Lastly the behavioral skills sessions will involve both active (role play, group critiques of recorded patient-provider interactions) and passive skills training (watching videos that demonstrate target skills). To reduce travel and time burden on provider participants, the training will be delivered in a hybrid format consisting of both in person, on-site training delivered at the offices of the GDCDC as well as self-directed online units for provider participants to complete on their own within a pre-specified window of time.

The main interactions associated with research activities in Stage 2 involve collection of follow-up data using the same face-to-face surveys and unannounced SP approach as in the baseline visits. The face-to-face survey will be administered by study staff with consented and enrolled providers to collect follow-up data on their attitudes towards working with marginalized populations. In addition consenting providers will have an unannounced SP dispatched to their clinic over the course of the observation period (between 1-3 months from the completion of the stigma reduction intervention) to collect data on observed clinical behaviors. As in the baseline round, SPs will present standardized cases with indications of early stage syphilis infection without informing provider participants that they are incognito patients. Immediately following the visits, SPs will report on the specifics of the encounter by responding to a standardized healthcare quality checklist administered to them by a study enumerator. Enumerators will not accompany SPs into the clinic but will instead wait nearby location such as inside the hired car used for transport to and from clinics. Provider will have been instructed not to confront any patient they suspect may be an SP, and to instead make note of the patient name and visit date. At the conclusion of the follow-up procedures, providers will be given an opportunity to ask whether a particular patient was in fact an SP, findings from which will be included in our study findings as an "SP detection rate."

## 5.0 Procedures Involved

### 5.1 *Study Design*

The design of the overall study is a pilot RCT to evaluate the preliminary effectiveness of the stigma reduction intervention developed in the course of the project, with randomization taking place at the facility level (cluster randomization). As activities related to the preparatory phase of research have been completed, the activities described below pertain only to the RCT phase.

### 5.2 *Study Procedures:*

As described in Section 1.1, study procedures relevant to the RCT Phase (Phase 2) to which this protocol pertains will be divided into the following two stages:

PROTOCOL TITLE: Standardized Patients to Address Intersectional Stigma  
VERSION DATE: 07/23/2019

**Stage 1: Implementation of the stigma reduction intervention.** The intervention will consist of three sections as informed by the Information-Motivation-Behavioral Skills model of behavior change as follows:

1. Information: this unit will consist of substantive information on a) clinical diagnosis and management of common STIs and b) HIV/STI epidemiology with a focus on its public health impact on the MSM population.
2. Motivation: this unit will include sessions exploring providers' intrinsic motivations for practicing medicine and use group discussions to explore their self-perceived roles in addressing the HIV/STI crisis, particularly in socially marginalized groups including MSM.
3. Behavioral skills: these sessions will involve both active (role play, group critiques of recorded patient-provider interactions) and passive skills training (watching videos that demonstrate target skills).

To reduce travel and time burden on provider participants, the training will be delivered in a hybrid format consisting of both in person, on-site training delivered at the offices of the GDCDC as well as self-directed online units for provider participants to complete on their own within a pre-specified window of time.

**Stage 2: Follow-up data collection using unannounced SP visits:** Immediately following the intervention, staff will conduct clinic visits to administer an in person survey of a shorter version of the baseline survey on their attitudes towards marginalized populations. Within 1-3 months the intervention, SPs will conduct a second round of unannounced clinic visits across the study facilities. As with the baseline visits, providers will not be informed that a particular visit is from an SP. Although all SPs will present to providers a standard case of presumptive syphilis, the case script used in each interaction will be randomly chosen from four slightly different versions that vary only in whether HIV or MSM status is revealed to providers. Draft versions of each of the SP case scripts are in Appendix 3.

The general protocol for SP visits will be as follows: SPs will be paired with an enumerator (members of the study team) to conduct clinic visits. Upon arrival enumerators will wait outside the clinic in the hired car while SPs will present at facilities using the pseudonym in the case script and be processed by clinic in-take staff according to standard local procedures. Before entering the clinic, enumerators will remind SPs of the names of any providers who have not consented to the study. If SPs are offered appointments with a non-consenting provider, they will follow a fixed script indicating their preference for a different "highly recommended" doctor for whose name they will feign a memory lapse. If a visit with a non-consenting provider cannot be avoided, the SP will accept the appointment but abort the visit immediately following intake (a not uncommon occurrence in the local setting). Once presenting to a consented provider, SPs will begin with the opening statement in the script which describes the patient's chief compliant/symptom. SPs will then use standardized language detailed in the case scripts to respond to provider questioning. In interactions where HIV or MSM status will be revealed, SPs will provide this information using standardized language, determined in the formative phase, immediately following the common opening statement. Study staff will accompany occasional SP visits to ensure adherence to protocol and will be available by phone throughout the audit to answer questions or troubleshoot unexpected problems.

PROTOCOL TITLE: Standardized Patients to Address Intersectional Stigma  
VERSION DATE: 07/23/2019

As in the baseline study procedures, SPs will exit facilities immediately following the visits and debrief with an enumerator in an area at some distance from the clinic (and most importantly out of earshot of any clinic staff or attendees) where enumerators will administer a health care quality checklist and conduct a debrief session with the SP. The health care quality checklist (Appendix 1) will be administered to SPs in a survey format and collect information on multiple dimensions of care quality including: adherence to Chinese clinical guidelines for syphilis prevention and management, clinical conduct, and communication. Debrief sessions with SPs will be guided by a structured interview guide to ensure each session covers the same content regarding SP perceptions of the clinical interaction.

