**Figure 1. Schemata for overall study design.**

Having completed all preparatory phase activities, this protocol will describe activities related to the **RCT phase** which will be conducted in two stages:

**Stage 1 of the RCT Phase: Implementation of the stigma reduction intervention.** A three-module provider training course designed during the preparatory phase will be administered to consenting providers employed at clinics randomized to the treatment arm of the study. The first module will be administered as a one-day training on site at the Guangdong Center for STD Control and Prevention. This will be followed by two online modules that provider participants will complete on their own. Design of this intervention has been informed by results of the baseline study and incorporates expert input from members of our community advisory boards (CAB), one made up of community members and the other of providers. Content of the intervention will include knowledge and skills training on topics including clinical management of common STIs, shared decision making, sexual history taking, and working with non-traditional/marginalized populations. Training methods for the onsite training will include didactic lectures, group-based discussion, and medical simulation and feedback with trained SPs. Methods for the online follow-up sessions will include webinars, short training videos, and multiple choice quizzes.

**Stage 2 of the RCT Phase: Follow-up data collection.** Follow-up collection using the same unannounced SP visit approach as in the baseline data collection will take place within 1-3 months of the end of the stigma reduction intervention. Briefly, this will consist of working with trained actors who are recruited from the community, who receive training to conduct unannounced clinic visits with consenting providers for the purposes of observing their clinical performance. SPs

will present clinically standardized case scenarios, but the HIV status and sexual orientation of each case will be randomly varied in order to quantify the extent to which HIV stigma and/or homophobia potentially contribute to the deterioration of care quality. Enrolled providers already provided their consent for both rounds of unannounced clinic visit during the preparatory phase of research.

Research activities in all phases of the project will take place in Guangzhou, China.

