By contrast our experimental SP audit method provides a window of insight into provider behaviors *as they unfold in real clinical settings*, providing an objective and standardized measure of stigma amenable to comparison across studies and settings. Our SPs will be recruited from among MSM living locally, whose group makeup will be managed to reflect the overall characteristics of the local MSM community in terms of age, ethnicity, and socioeconomic status. SPs will be trained to consistently present a standardized case to providers. Using an experimental audit design, we will randomly vary the HIV infection status and sexual orientation of all of our SPs. Stigma will be evaluated by comparing the quality of care that SPs experience during provider visits. Quality of care will be measured by administration of a standard of healthcare checklist to SPs following each visit, and which will include items related to provider behaviors including the types of questions asked, accuracy of the preliminary diagnosis, body language and bedside manner (checklist included in Appendix 1). Differences in tallied aggregate scores across SP visit scenarios (e.g. HIV positive versus HIV negative presentations) will be quantified as the enacted healthcare stigma attributable to the condition in question (i.e. HIV infection). In addition, SPs will participate in post-visit “debrief sessions” with another member of the study staff immediately following each visit to recount any other possible features of the visits—both positive and negative—not accounted for in the healthcare quality checklist. This method of quantifying stigma will not be used to identify individual providers or

PROTOCOL TITLE: Standardized Patients to Address Intersectional Stigma  
VERSION DATE: 07/23/2019

instances of poor treatment but rather to characterize population level incidence and patterns of stigma enacted by providers towards vulnerable patients. Lastly, the impact of the intervention on overall HIV testing volumes in study facilities will also be evaluated by examining aggregate counts of facility-level HIV tests conducted during the baseline and follow-up observation periods. This information will be provided by the laboratory departments of all participating facilities. This technique of data collection has been successfully piloted with a clinic-based intervention administered by the GDCDC.

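### Status is volunteered before any provider question, yet one 38-item score serves all four scripts: any item that disclosure makes redundant would be counted as HIV or MSM stigma

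*Combined protocol and SAP*

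**What the plan says.** Section 5.2 describes the case scripts as "four slightly different versions that vary only in whether HIV or MSM status is revealed to providers". Where a status is revealed, "SPs will provide this information using standardized language, determined in the formative phase, immediately following the common opening statement". The referent script reveals neither.

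The checklist is described in two places. Section 2.1 calls it an instrument "which will include items related to provider behaviors including the types of questions asked, accuracy of the preliminary diagnosis, body language and bedside manner". Section 5.2 says it covers "adherence to Chinese clinical guidelines for syphilis prevention and management, clinical conduct, and communication".

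Section 3.1 builds the primary index from 38 items of the post-visit questionnaire, "which is calculated as a weighted average of all 38 items". The weights come from a single inverted covariance matrix, and every item enters for every visit.

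Section 17.1 defines stigma as the difference in the mean of this index between scripts. Section 17.3 estimates it by β1 (HIV), β2 (MSM) and β3 (the excess when both are present). Section 17.3 also says that the effect of main interest is how training changes the between-script difference, estimated by arm-by-script terms α11 to α13. Among the topics taught, Section 1.1 lists "shared decision making, sexual history taking, and working with non-traditional/marginalized populations".

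**The concern.** The contrast between scripts measures stigma only if equal care earns an equal score in each script. The scripts do not leave the provider with the same things to find out. Suppose an item gives credit for asking the sex of partners, or for advising an HIV test. It can be earned in the referent visit. After the matching disclosure it may be answered already, or no longer indicated. A provider who leaves it out has not treated that patient worse, but the index falls.

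Nothing in Sections 3.1, 5.2 or 17.3 deals with this. There is no script-specific scoring, no not-applicable code and no credit for information already volunteered. The Section 3.1 formula needs a value for all 38 items in every visit. Skip patterns appear in Section 17.4 only as a feature of the survey software, with no link to script or scoring.

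What is at stake is the meaning of β1 and β2, of the total contrast between the dual-status and referent scripts, and possibly of the training-by-script terms.

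**Working it through.** The plan gives no figure for this artefact, so there is none to reproduce. The steps below trace which estimates are exposed and then give an illustrative size.

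**1. Which estimates carry it.** Let a_H be the index points lost to items made redundant by HIV disclosure, and a_M those lost to MSM disclosure, with no true stigma. Relative to the referent script:

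- HIV only: −a_H, so β1 is shifted by −a_H.
- MSM only: −a_M, so β2 is shifted by −a_M.
- Both: −(a_H + a_M), so the total dual-status contrast carries the sum.
- β3 = −(a_H + a_M) + a_H + a_M = 0, so losses specific to one attribute cancel.

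An item made redundant by either attribute is lost once, not twice, in the dual script. It leaves a residue in β3 equal to its own loss, with positive sign. Hence β3 is largely, not wholly, protected.

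**2. Overall intention-to-treat effect.** If scripts are balanced across arms, the loss in disclosing visits is common to both arms and does not by itself bias the arm comparison.

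**3. Size with equal weights.** Assumptions, none of them in the documents: 38 yes/no items with mean 0.4; inter-item correlation ρ from 0.05 to 0.2; k affected items, asked with probability 0.5 in the referent script and 0 after disclosure.

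- Index SD = √[0.4 × 0.6 × (1 + 37ρ) / 38] = 0.134, 0.172 and 0.230 for ρ = 0.05, 0.1 and 0.2.
- False gap in SD units = (k × 0.5 / 38) / SD.

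| k | ρ = 0.05 | ρ = 0.1 | ρ = 0.2 |
|---|---|---|---|
| 0 | 0 | 0 | 0 |
| 1 | 0.10 | 0.08 | 0.06 |
| 2 | 0.20 | 0.15 | 0.11 |
| 3 | 0.29 | 0.23 | 0.17 |

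A fall to 0 is the extreme. If asking falls only from 0.5 to 0.25, each entry halves: about 0.03-0.05 for one item and 0.09-0.15 for three.

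**4. Size with the Section 3.1 weights.** A simulation used 160 visits, 40 per script, 400 runs, ρ = 0.1, the same fall from 0.5 to 0, and no true stigma. Items were scaled to their referent-script SD, and the same k items were lost in all three disclosing scripts. The mean false gap was about 0.41, 0.56 and 0.66 SD for k = 1, 2 and 3, and about 0 (−0.005) for k = 0. The equal-weight figures may therefore be too small, but these also rest on the extreme fall.

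**5. Yardstick.** Section 17.2 names 0.18 and 0.17 SD as minimum detectable effects. They are used here only as the plan's own idea of a small effect. They do not reproduce from 160 visits: 80 against 80, two-sided, gives (1.96 + 0.84) × √(2/80) ≈ 0.44 SD.

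**6. Training-by-script terms.** With script main effects in the model, a loss equal in both arms cancels (simulated interaction about 0). A loss that training changes does not cancel. If training raised the asking of the k items by 0.3 in the referent script only, the equal-weight shift would be (k × 0.3 / 38) / SD: 0.03-0.06 SD for k = 1, 0.07-0.12 for k = 2 and 0.10-0.18 for k = 3. The simulation gave about 0.18 to 0.34 SD for one to three items. In both, the shift is towards an apparently wider stigma gap.

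The arm-by-script equation as printed has SP fixed effects but no script main effects. Read literally, α11 to α13 are then script gaps within the trained arm, and they would carry the whole artefact. The preceding ITT model does include script effects, so this may be a drafting slip. It is a separate point.

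**The case against.** The strongest reply is that the defect depends on an instrument nobody can inspect here. Appendix 1 is not in the text reviewed, which is no fault of the plan. No section shows that any of the 38 items is redundant in any script. The description in Section 2.1 covers the whole checklist, while the 38 items may be a selection from it. Item coding could sit in the instrument, which the revision history says was revised together with the scripts. This stands in full: the point is conditional.

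Second, disclosure rarely removes all reason to ask. Announcing same-sex behaviour does not say whether there are female partners too, and a declared HIV infection does not say when or where the test was done. Most other questions stay equally relevant. This also stands, and it is why a fall to 0 is called extreme and k = 1 is shown.

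Third, the sign is not certain. Disclosure may prompt extra questions or advice, and the training also covers work with marginalised groups, which could raise scores in disclosing visits. A reader might infer that effective training will look as if it increased stigma. The documents do not support that, because it needs a rise in asking confined mainly to the referent script. A reader might also infer that every dual-status estimate is contaminated. Step 1 shows that β3 is largely spared.

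What the reply does not meet is the scoring rule itself. Section 3.1 states a single all-item formula, and no section says what happens to an item that the script has already answered.

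**Conclusion.** The point holds as a conditional one. Disclosure precedes questioning, the checklist scores questions asked, and one 38-item score defines stigma with no applicability rule. For any item made redundant by disclosure, β1, β2 and the total dual-status contrast would include a difference that is not unequal care. β3 is largely protected, and the overall arm comparison is unaffected if scripts are balanced across arms. The training-by-script terms are at risk only if training changes the asking of those items differently across scripts, in a direction that cannot be fixed in advance.

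Under the extreme equal-weight assumptions, two or three affected items could produce a false gap of the same order as the 0.17-0.18 SD named in Section 17.2. One would produce about 0.06-0.10 SD, and none would produce nothing. The weights in Section 3.1 could make it larger. The documents do not support the stronger statement that the stigma estimates are in fact biased, because the number of affected items is unknown here. The sponsor holds the checklist and can settle it.

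**What to change.** In Section 3.1, before follow-up outcomes are analysed by arm:

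- List the items whose answer or indication is directly supplied or removed by the announced HIV or MSM status, with a one-line reason for each.
- Leave those items out in all four scripts, at baseline and follow-up, for the stigma contrasts and for the training-by-script model in Section 17.3. Recompute the weights on the retained items.
- Keep every item that stays equally indicated after disclosure, since unequal treatment may show there.
- Keep the full 38-item index for the overall arm comparison, and report the full-index stigma contrasts as a sensitivity analysis.

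The cost is one classification exercise and a few lines of text; no script, visit or data collection changes. The index for the stigma contrasts becomes slightly shorter and slightly less reliable, and classifying items takes some judgement, which is why it should be fixed in advance. Section 2.1 says that baseline stigma results have already been shared with the advisory boards, so the recomputed baseline values should be shown beside the full-index ones. If no item qualifies, one sentence saying so closes the point.
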